8.3 Analysis plan for anti-drug antibodies (ADA) data

The purpose of this appendix is to provide a general reference for the analysis of ADA data in this study. The complete set of presentations described in this appendix will be conducted.

Serum samples for ADA assessments will be conducted utilizing a tiered approach (screen, confirm, titre) and ADA data will be collected at scheduled visits shown in the CSP. ADA result from each sample will be reported as either positive or negative. If the sample is positive, the ADA titre will be reported as well. In addition, the presence of neutralizing antibody (nAb) will be tested in all ADA-positive samples using a ligand-binding assay. The nAb results will be reported as positive or negative.

For each patient, the following responses variables will be evaluated:

- ADA positive at any visit (including baseline and/or post-baseline) (ADA prevalence)
- ADA positive at both post-baseline and baseline
- ADA positive at post-baseline only (treatment-induced ADA positive)
- Baseline ADA titre increased by >4-fold at ≥ 1 post-baseline timepoint (treatment-boosted ADA positive)
- ADA positive at baseline only
- ADA persistently positive, where persistently positive is defined as at least 2 post-baseline positive ADA measurements with at least 16 weeks (112 days) between the first and last positive measurement or a positive ADA result at the last available post-baseline assessment
- ADA transiently positive, defined as ADA negative at baseline and at least one post-baseline ADA positive measurement and not fulfilling the conditions for persistently positive
- Treatment-emergent ADA positive, defined as either treatment-induced ADA positive or treatment-boosted ADA positive (ADA incidence)
- nAb positive at any visit (applicable for ADA-positive patients only)

All analyses will be conducted on the safety analysis set and by treatment group unless otherwise specified. All ADA results will be listed.

8.3.1 ADA results during the study

The numbers and percentages of patients with ADA responses listed above during the study will be summarised by treatment group. The number and percentage of treatment-emergent ADA positive patients will be computed as the sum of treatment-induced and treatment-boosted ADA positive patients. No formal hypothesis testing will be conducted.

The maximum titre across the different visits (including both baseline and post-baseline measurements) will be summarised by descriptive statistics (n, minimum, quartiles [Q1, median and Q3] and maximum). The number and percentage of ADA positive patients with

maximum titre \leq and $>$ the median of maximum titres will be also summarised respectively. The median of maximum titre will be calculated based on the maximum titre of each ADA positive patient within each treatment group.

The key patient information will be listed for patients with positive ADA results only. This listing will include but not be limited to a patient's ADA result, sample collection date, days from previous dose, number of active doses received, titre result, nAb status, benralizumab concentration, and eosinophil counts. A listing of all collected ADA results (including ADA negative) will also be provided.

8.3.2 ADA results by visit

ADA response (positive or negative) and the titre values will be summarised at baseline and at all scheduled post-baseline visits by treatment group. In the event a patient has more than one titre result within a given visit window, the maximum ADA titre will be used in the by-visit summary. A line plot of proportion of patients who are ADA positive by visit will also be provided.

8.3.3 ADA and eosinophil levels

Blood eosinophil counts will be summarised by visit for ADA positive patients, ADA negative patients, treatment-emergent ADA positive patients, ADA positive with titre $>$ median of maximum titre, ADA persistently positive patients, and nAb positive patients, using the following descriptive statistics: n, mean, standard deviation, median, Q1, Q3, minimum and maximum. A line plot of eosinophil counts by visit and ADA status will also be presented.

8.3.4 nAb response

nAb response (positive or negative) will be summarised by visit for ADA positive patients.

8.3.5 ADA and efficacy

The effect of ADA on the primary endpoint (annual asthma exacerbation rate) and 2 key secondary endpoints (change from baseline in pre-bronchodilator FEV₁ and change from baseline in total asthma symptom score) will be evaluated by treatment group and ADA subgroups (ADA positive, ADA negative, treatment-emergent ADA positive, ADA persistently positive, nAb-positive, and ADA positive with titre $>$ median of maximum titre). Due to the expected small number of ADA positive patients in the placebo group, no formal statistical analysis on efficacy (benralizumab vs. placebo) by ADA status (positive/negative) is planned.

The following analyses will be performed:

- ADA and exacerbation rate: The descriptive summary statistics of the annualised exacerbation rate by ADA subgroups will be provided.

- ADA and pre-bronchodilator FEV₁: The descriptive summary statistics of the change from baseline in pre-bronchodilator FEV₁ by ADA subgroups will be provided.
- ADA and total asthma symptom score: The descriptive summary statistics of the change from baseline in total asthma symptom score by ADA subgroups will be provided.

For calculation of the annual exacerbation rate, the follow-up time for exacerbation will be defined as in Section 3.2. For pre-bronchodilator FEV₁ and total asthma symptom scores, the last valid non-missing observation by EOT visit or IPD visit will be included in the calculation.

8.3.6 ADA and safety

The effect of ADA on safety will be examined by descriptive summaries.

AE and SAEs during the study (separately for on-treatment and on-study periods) will be summarised. The on-treatment and on-study periods are defined Section 3.6.1. The AE will also be evaluated by causality. The potential impact of ADA on hypersensitivity will be assessed.

The summaries will be presented for ADA positive patients, ADA negative patients, ADA positive patients with titre > median of maximum titre, ADA persistently positive patients, nAb positive patients, and treatment-emergent ADA positive patients.

8.3.7 ADA and PK

Benralizumab serum concentrations will be summarised by visit for ADA positive patients, ADA negative patients, treatment-emergent ADA positive patients, ADA positive patients with titre > median of maximum titre, ADA persistently positive patients, and nAb positive patients.

8.4 Analyses to assess the impact of the COVID-19 pandemic

Additional analyses and summaries will be produced to assess the impact of the COVID-19 pandemic on the primary results. The analyses and summaries are detailed below, referencing the section of this SAP to which they relate to.

COVID-19 phases (pre- / during-)

The start date of COVID-19 pandemic will be defined at a country level: 29th January 2020 (the date China declared COVID-19 to be a national public health crisis, i.e., significant emergent public health grade one response started across China mainland provinces) for China mainland, and 11th March 2020 (the date WHO declared COVID-19 to be a pandemic) for non-China countries and Taiwan.

Data recorded before the start date will be *pre-pandemic*. Data recorded on or after the start date will be *during-pandemic*, as the end date of COVID-19 pandemic is not defined.

Violations and deviations

The important PDs will be summarised and listed together, including COVID-19-related and non-COVID-19-related important PDs (see Section 2.3.1). An additional summary will present COVID-19-related important PDs and non-COVID-19-related important PDs separately, by treatment group, for the FAS. A separate listing will be produced, including all COVID-19-related PDs (important and non-important) by treatment group.

COVID-19-related study disruptions

A COVID-19-related study disruption is any important change in the study conduct or data collection due to the COVID-19 pandemic. COVID-19-related study disruptions may include, but not necessarily be limited to:

- Changes to visit schedules, missed visits, changes to visit procedures;
- Discontinuation of IP, missed IP, changes to IP administration;
- Discontinuation of study.

An additional table will summarise all COVID-19-related study disruptions by treatment group for the FAS. The number and percentage of patients with at least one COVID-19-related study disruption will be reported. A listing of all COVID-19-related study disruptions will be produced with details.

The number and percentage of patients randomised pre-pandemic and during-pandemic will be reported, respectively. Total pre-pandemic and during-pandemic follow-up times will be presented in total patient-years, and also as proportions of total overall follow-up time, as an indication of the proportion of study time potentially affected by COVID-19. The overall follow-up time is the duration between the date of randomisation and the date of study completion or withdrawal from study, inclusive.

The number and percentage of patients who missed at least one IP dose due to COVID-19, the number and percentage of patients missing 1, 2, and ≥ 3 doses due to COVID-19, and the number and percentage of patients with consecutive missed doses due to COVID-19 will be presented. The number and percentage of patients who had at least one IP dose delayed due to COVID-19 will also be presented.

The number and percentage of patients with at least one scheduled visit impacted due to COVID-19 will be summarised by treatment group. Impacted visits will be classified as “missed scheduled visit”, “delayed scheduled visit” or “changed format of scheduled visit”. “Changed format of scheduled visit” will be further classified by as “On-site only, partially completed”, “Remote visit (Audio or Video) only”, and “Both remote and on-site used”.

The number of patients discontinuing IP or withdrawing from the study due to COVID-19 will also be summarised by treatment group.

Kaplan-Meier plots will be produced summarising separately the time (in weeks) to first visit impacted by COVID-19 and to first IP dose missing due to COVID-19.

- Time to first visit impacted by COVID-19 = [intended date of the first impacted visit – date of randomisation] + 1, where the intended date is based on the visit schedule listed in the protocol. Patients who did not have any visits impacted by COVID-19 will be censored at the date of study completion or study withdrawal.
- Time to first IP dose missing due to COVID-19 = [intended date of the first missed IP dose – date of randomisation] + 1, where the intended date is based on the visit schedule listed in the protocol. Patients who did not have any IP dose missing due to COVID-19 will be censored at the date of last dose of IP.

Analyses of the primary endpoint

Two additional sensitivity analyses of the primary endpoint will be carried out to compare annual asthma exacerbation rates in the benralizumab group with those in the placebo group during the pre-pandemic phase and the during-pandemic phase respectively. The first analysis will use the pre-pandemic data only, i.e., all observed data over the 48-week treatment period (see Section 3.2) up to and including the day prior to the start date of pandemic. The second analysis will use the during-pandemic data only, i.e., all observed data from the start date of pandemic until the end of 48-week treatment period. These analyses will use all observed data in the specific COVID-19 phase regardless of adherence to randomised treatment or the use of an alternative treatment.

All these sensitivity analyses will use the similar negative binomial model as specified for the primary analysis (see Section 4.2.5.1). The response variable will be the number of exacerbations experienced by a patient during the follow-up for exacerbation in the specific COVID-19 phase. The logarithm of the patient’s corresponding follow-up time in the specific COVID-19 phase will be used as an offset variable in the model. The model will include

covariates of treatment group, region (China/Non-China), number of exacerbations in the year before the study, and the use of maintenance oral corticosteroids (yes/no).

Asthma exacerbation summary statistics as described in Section 4.2.5.2 will also be repeated by pandemic phase: pre-pandemic, during-pandemic.

AEs

All AE-related analyses described below will be based on the safety analysis set using the on-treatment period (see Section 3.6.1).

The overall AE summary table (AEs in any category reported) will be repeated by pandemic phase: pre-pandemic, during-pandemic. Categories will include: any AEs, SAEs, AEs with outcome of death, DAEs, COVID-19 AEs (as defined by standardised MedDRA query of COVID-19 based on the latest MedDRA version) and non-COVID-19 AEs.

Summaries of AEs and SAEs by SOC and PT along with the rates per patient-years at risk will be provided by pandemic phase: pre-pandemic, during-pandemic. Summaries of COVID-19 AEs and non-COVID-19 AEs by SOC and PT along with the rates per patient-years at risk will be provided for the during-pandemic phase.

If there are more than 10 patients reporting COVID-19 AEs, then the AE listing will be repeated including only these patients, with details of all AEs reported by these patients.

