1.2 Study design

This is a randomised, double-blind, parallel group, placebo-controlled study designed to evaluate the efficacy and safety of a fixed 30 mg dose of benralizumab administered subcutaneously for patients with a history of asthma exacerbations and uncontrolled asthma receiving medium to high-dose ICS/LABA with or without OCS and additional asthma controllers.

Approximately 666 patients will be randomised, of which at least 70% patients will be from China (including the mainland of China and Taiwan). The randomisation will be stratified by country/region (the mainland of China, Taiwan, South Korea or Philippine), age group (adult or adolescent), and peripheral blood eosinophil count at time of Visit 1 (<300 or \geq 300 cells/ μ L).

All the patients will be randomised to either placebo or benralizumab in a 1:1 ratio, every 4 weeks for the first 3 doses and then every 8 weeks thereafter. Study recruitment will be closed when recruitment is closed for all strata, based on the following strata closure process:

1. The eosinophil <300/ μ L stratum will be closed to the patients from China when the total number of Chinese patients in the eosinophil <300/ μ L stratum reaches approximately 166.
2. The eosinophil <300/ μ L stratum will be closed to the patients from all countries when the total number of patients in the eosinophil <300/ μ L stratum reaches approximately 222.
3. The whole study will be closed for recruitment when the total number of patients in the eosinophil \geq 300/ μ L stratum reaches approximately 444, with at least 70% Chinese patients in the stratum.

After initial enrolment and confirmation of entry criteria, patients will proceed to the run-in period of a minimum 4 weeks to allow adequate time for all of the eligibility criteria to be evaluated. Patients who meet eligibility criteria will be randomised to a 48-week treatment period. Patients will be maintained on their currently prescribed medium to high-dose ICS/LABA therapy and other asthma controllers, without change, from visit 1 until the end of the study.

A follow-up visit will be conducted at Week 56.

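### The Kaplan-Meier plot of first IP dose missed due to COVID-19 times events by the intended schedule but censors at the actual last dose, so its final step is too high if last doses are given early

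*SAP*

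**What the plan says.** Appendix 8.4 defines the event time from the "intended date of the first missed IP dose", "where the intended date is based on the visit schedule listed in the protocol", minus the randomisation date, plus one. For everyone else the rule is: "Patients who did not have any IP dose missing due to COVID-19 will be censored at the date of last dose of IP". The word for an intended date, used twice in the event definition, is absent from the censoring rule, so the natural reading is the date on which the dose was actually given.

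Section 1.2 gives the dosing as "every 4 weeks for the first 3 doses and then every 8 weeks thereafter", over a 48-week treatment period.

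The same appendix gives examples of COVID-19 disruption, one line of which reads "Discontinuation of IP, missed IP, changes to IP administration". It does not say whether the doses not given after a COVID-19 discontinuation are themselves missing due to COVID-19 for the purpose of the plot.

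**The concern.** In a Kaplan-Meier estimate, a patient known to be event-free at a given time must be in the risk set at that time. Here a patient who received the final dose is known not to have missed it. If that dose came before its intended day, the patient is censored on the earlier, actual day and is gone when the misses of that same dose are counted. Those misses are then divided by a risk set from which the early attenders have been removed.

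The mismatch works in one direction only. A last dose given on or after its intended day leaves the patient in the risk set; one given early removes the patient. The final step can be inflated by this mechanism but never lowered. The curve could also disagree with the table planned in the same appendix of patients who missed at least one dose because of COVID-19, for no reason other than attendance a few days early.

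Elsewhere the SAP keeps to one clock: the plot of time to study treatment discontinuation in Section 4.2.1 uses actual dose dates for both events and censoring.

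**Working it through.** The SAP states no figure for this curve, so there is none to reproduce. The check is of the rule, with assumed inputs.

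**Inputs from the SAP**
- 666 patients randomised 1:1 (Section 1.2), so 666/2 = 333 per arm.
- The dosing pattern of Section 1.2 implies doses at Weeks 0, 4, 8, 16, 24, 32 and 40. Week 40 as the last dose is an inference, because the SAP does not list dosing visits. Section 3.1.3 (Table 1) puts Week 40 at Day 281. The mechanism does not depend on which dose is last.

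**Inputs assumed (not in the SAP)**
- The share of patients who miss a dose because of COVID-19, and the spread of actual dosing days around the intended day.

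**Step 1: the final step alone.** Let N patients be due the last dose, of whom d miss it because of COVID-19, and let f be the share of the others dosed before the intended day. The correct step is d/N. The rule as written gives

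step = d / [(N − d)(1 − f) + d].

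With N = 333 and d = 10, the correct value is 10/333 = 3.0%.

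| f | Risk set | Step |
|---|---|---|
| 0 | 333 | 3.0% |
| 0.20 | 323 × 0.80 + 10 = 268.4 | 3.7% |
| 0.47 | 323 × 0.53 + 10 = 181.2 | 5.5% |
| 0.60 | 323 × 0.40 + 10 = 139.2 | 7.2% |

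**Step 2: the whole curve.** Take a 2% miss probability at each of the six post-baseline doses and no dropout.
- True cumulative proportion: 1 − 0.98^6 = 11.4%.
- Last dose uniform over the 15 days from −7 to +7: 7/15 of patients are early and 8/15 are not. Final step = 0.02 / (0.02 + 0.98 × 8/15) = 0.02/0.5427 = 3.7% instead of 2.0%.
- Curve end: 1 − 0.98^5 × (1 − 0.0369) = 1 − 0.9039 × 0.9631 = 12.9%.
- With ±3 days, 3/7 are early: final step 0.02 / (0.02 + 0.98 × 4/7) = 3.4%, and the curve ends at 1 − 0.9039 × 0.9655 = 12.7%.
- With every last dose on its intended day, the final step is 2.0% and the curve ends at 11.4%: no bias.

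A simulation of 60,000 patients agrees: 12.9% under the SAP rule with ±7 days, and 11.4% once censoring is moved to the intended date of the last dose received. Without dropout, the steps before the last are unaffected, because those patients have later doses and remain at risk.

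**Step 3: the open rule on COVID-19 discontinuation.** Add a 1% chance per dose of stopping IP because of COVID-19, with the 2% miss chance and ±7 days as before. If such patients are censored at their last dose, the simulated curve ends at 13.0% under the SAP rule, or 11.5% with the dates aligned. If the first dose not given counts as an event, the aligned curve ends at 1 − 0.97^6 = 16.7%. Two programmers following the text could produce either version.

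**The case against.** The strongest reply is that little hangs on this plot. Appendix 8.4 also tabulates patients who missed any, one, two, three or more, or consecutive doses because of COVID-19, so the cumulative proportion need not be read off the last step; the plot mainly adds timing. The size above rests wholly on assumed timing and miss rates. All of this stands. It limits the importance of the point, but the two dates are still on different clocks.

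Four stronger readings are tempting, and the documents do not support them.

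- *Patients who stop because of COVID-19 go uncounted.* They do not: "The number of patients discontinuing IP or withdrawing from the study due to COVID-19 will also be summarised by treatment group", and "A listing of all COVID-19-related study disruptions will be produced with details". At most they are absent as events from this one curve.
- *The SAP censors these patients.* That is one reading. Listing discontinuation and missed IP as separate examples makes it plausible, but the censoring rule covers only patients with no dose missing due to COVID-19, and the SAP does not say whether a dose lost after a COVID-19 stop is such a dose. If they are censored, the curve understates disruption, which is opposite in direction to the date mismatch. The curve as a whole therefore need not be too high.
- *The companion plot of first impacted visit has the same fault.* There, "Patients who did not have any visits impacted by COVID-19 will be censored at the date of study completion or study withdrawal". A fault would arise only if study completion were dated at an early last visit, and the SAP does not define that date closely enough to show it.
- *The arms could be distorted differently.* In a randomised, double-blind trial nothing in the SAP suggests that early attendance differs systematically by arm; only chance differences remain.

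**Conclusion.** The point holds for the date mismatch. As written, the censoring rule inflates the final step of the missed-dose curve whenever fully dosed patients receive their last dose before its intended day. Under the assumed 2% per dose and a uniform ±7-day spread, the curve ends at about 13% instead of 11.4%. The excess is smaller if fewer last doses are early and nil if none is. This rests on reading the censoring date as the actual one, which the wording favours.

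The treatment of COVID-19 discontinuation in the plot is an ambiguity to be settled, not a demonstrated error. The matter is minor: the plot is descriptive, carries no test, and does not bear on the primary or key secondary analyses.

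**What to change.** In Appendix 8.4, censor patients with no COVID-19 missed dose at the protocol-intended date of the last dose they received, so that events and censoring follow the same schedule. Add one sentence saying whether the first scheduled dose not given after a COVID-19 discontinuation of IP counts as missing due to COVID-19 in this plot. Either answer is workable, but counting it as an event makes the plotted quantity a composite of missed and stopped, and the plot title should then say so.

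The cost is two sentences and a small programming change. No new data are needed, and no other analysis changes.

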8.5 OCS conversion factors for prednisone equivalents

Total daily OCS dose will be converted to a prednisone equivalent using the following table:

Table 10 Estimated OCS dose therapy equivalence

Oral Corticosteroid	Approximate equivalence dose
Prednisone	10 mg
Prednisolone	10 mg
Cortisone	50 mg
Hydrocortisone	40 mg
Methylprednisolone	8 mg
Triamcinolone	8 mg
Betamethasone	1.2 mg
Dexamethasone	1.5 mg
Deflazacort	12 mg

For example, to convert a cortisone total daily dose to a prednisone equivalent total daily dose, a multiplication factor of $0.2 = 10/50$ should be used.

